- *Confidentiality Safeguards:* To ensure confidentiality, all information will be coded so that it cannot be associated with any individual. A master sheet, with individual names and their respective code numbers will be kept in a locked file that can be accessed only under supervision of the Principal Investigator. All data entered into the computerized database will be identifiable by subject code number only. No one other than the Principal Investigator and the study coordinating team (TBA coordinator) will have access to records identifying subjects' names at any time. However, the facilitators will not have access to the data collected as part of the assessment. The information gathered will be used only for scientific, educational, or instructional purposes.
- *Mandatory Reporting Safeguards:* Procedures to prevent the violation of confidentiality in accordance with reporting requirements are limited by the mandatory nature of these requirements. Subjects are informed in the consent document that staff must report to authorities 1) physical injury caused by other than accidental means, as required by ORS 419B.005 through 419B.040; and 2) information from a study participant which leads staff to believe a person is in imminent danger of physical harm.
- *Staff Training Safeguards:* Every personnel on the study will be required to complete the CITI-Core course, an extensive, training/testing program which focuses on good clinical practice, to be certified by the IRB at the University of Texas. Study personnel will also have to be re-certified on a biannual basis by completing the CITI-CE course.
- Research staff receive training specific to each assessment/measurement tool until they meet criteria for each assessment administration procedure. All project staff will meet on a weekly basis for ongoing training, monitoring of protocol, and problem solving. Questions regarding data collection will be promptly referred to the PI.
- Research staff as well as facilitators will be trained to identify events that would fall under mandatory reporting guidelines. These include physical injury to any study subject caused by other than accidental circumstances or information from a study participant that leads staff to believe a person is in imminent danger of physical harm.

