Staff must report two kinds of events that are potentially harmful to participants or others: adverse events and serious adverse events.

Adverse Events

Adverse events are those events that create distress for participants, such as (1) family crises; (2) possible violations of confidentiality; (3) extreme distress caused by assessment procedures; and extreme embarrassment or distress in response to disclosing sensitive personal information. Adverse events that are not serious will be logged into the project's adverse events folder and noted in the participant's study file. Serious adverse events will be logged and notated, and they will be reported to the PI immediately. A Serious Adverse Event form will be completed and sent to the Institutional Review Board of the University of Texas as well as the NIH project officer within 2 business days.

1. Family crises

Family crises involve a range of situations that threaten the ability of parents to provide essential support for their children and also include domestic violence or marital crisis, symptoms of mental illness in parents (e.g., depression and mania), and family environmental changes (e.g. homelessness).

Assessment staff: Project staff will be trained by Co-I [name] and PI [name] to recognize signs of family crises and to consult with the PI. Together they will determine the best response to the patient's needs, including referral, if so indicated. Project staff will be trained to recognize symptoms of severe problem

behavior, extreme family disagreements, domestic violence, marital crisis, and mental illness. Participants in the project will have emergency numbers to call if there is a crisis situation involving the parent's use of the curriculum tools that may have resulted in a problem situation that escalates, such as violence to others in the household.

2. Possible Violations of Confidentiality

When any staff member becomes aware that participant confidentiality has been violated, the staff member is required to report this to the PI. The PI will then meet with the staff member who violated confidentiality, will review the information and determine next steps. If the suspected staff member is found to have violated participant confidentiality, the staff member will be terminated. The incident will be reported to the University of Texas IRB and to the NIH project officer within 5 business days.

3. Extreme Distress Caused by Assessment Procedures

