In cases where a participant reports or displays extreme distress in response to assessment/measurement procedures/battery, the assessment will be discontinued immediately. Staff will be trained to identify and handle signs of participant distress and will contact the project facilitator(s) and /or PI who will assess the participant's distress level and will refer her/him to counseling if necessary. In cases of extreme distress caused by assessment procedures, a notation will be made in the participant's study file.

4. Extreme Embarrassment or Distress in Response to Disclosing Sensitive Personal Information

If a participant reports or displays extreme embarrassment or distress in response to requests for sensitive personal information (e.g. eating behavior, other psychopathology), the assessor will discontinue the assessment and will refer the participant to counseling if necessary. In cases of extreme embarrassment or distress caused by disclosing sensitive personal information, a notation will be made in the participant's study file and the study coordinator will be notified.

Serious Adverse Events

Serious adverse events refer to events that place participants or others in imminent danger. Such events include suicidal ideations or intentions, instances of physical abuse, neglect or threat of physical harm among participants to themselves or others. Other serious adverse events, in which harm to participants or others has already occurred, must also be reported. Such events include hospitalization or death. To anticipate these concerns, the project has established procedures and guidelines to respond to risk disclosures and crisis situations among subject families. Assessment staff will be trained to recognize risks or crises that require immediate reporting response. Five types of situations require special procedures:

1. Suicidal Thoughts or Attempts

Two types of risks will be addressed in the project: (a) ideation or the presentation of thoughts or interest in suicide, and (b) action, which includes both thoughts of suicide as well as the presence of a plan and means to accomplish a suicide act.

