The participants will complete all self-report measures in conjunction with direct entry onto a laptop. The research coordinator will be required to review identified instruments and items for response values that indicate suicidal ideation or plans for action. Based on the response, the coordinator will be required to review disclosure information with the PI and, if deemed necessary, conduct follow-up inquiry with the participant to further determine level of risk. If the participant is determined to present immediate risk of suicidal action, one of the staff facilitators, will develop a safety plan with the client and make indicated referrals. In the most extreme cases of risk, the staff facilitator assumes follow-up responsibility for the plan of action with the family.

2. Abuse

Child/adolescent or spousal/partner abuse concerns may arise from any or a combination of the following sources: (a) the participant verbally indicates that abuse has occurred or is occurring, or (b) the participant is observed with bodily injury (e.g. bruises, burns, black-eyes) whose origin appears to differ from the explanation given of the injury. Abuse is considered a serious adverse event because it represents an imminent danger to the person.

At any time during the assessments, if any of the above information leads staff to suspect abuse or neglect, steps are outlined for staff to obtain additional information, document the information in the participant's study file and contact the study coordinator. Based on the information, the coordinator will advise the PIs and follow-up regarding communication to the family, appropriate further inquiry, follow-up, and reporting. The PI will be notified to review the information and determine next steps. If abuse is

indicated, the project coordinator will report abuse to protective services on behalf of the participant.

3. Threat of Danger to Others

The threat of danger to others includes disclosure of potential physical harm by a participant to others, including members of the participant's family or other individuals in the community.

At any time during the assessment, if any information derived lead staff to suspect a participant poses a threat of harm to others, steps are outlined for staff to obtain additional information, document the information and contact the PI.

4. Hospitalization

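### The consent, as the protocol describes it, gives a narrower limit on confidentiality than the abuse procedure applies

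*Combined protocol and SAP*

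**What the plan says.** Four places in the combined protocol and SAP bear on this.

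- **Data and Safety Monitoring, Mandatory Reporting Safeguards.** The consent document is said to inform subjects that "staff must report to authorities 1) physical injury caused by other than accidental means, as required by ORS 419B.005 through 419B.040" and, as item 2, "information from a study participant which leads staff to believe a person is in imminent danger of physical harm". The list is numbered and has no wording that leaves it open.
- **Staff Training Safeguards.** Research staff and facilitators are trained to identify events under the mandatory reporting guidelines: "These include physical injury to any study subject caused by other than accidental circumstances", followed by the same imminent-danger item.
- **Response procedures for adverse events, Serious Adverse Events (introduction).** Serious events are defined by the imminence of danger to a participant or another person: "Such events include suicidal ideations or intentions, instances of physical abuse, neglect or threat of physical harm among participants to themselves or others". On training it adds: "Assessment staff will be trained to recognize risks or crises that require immediate reporting response".
- **Serious Adverse Events, item 2 (Abuse).** Concern may arise from a participant saying that abuse has happened or is happening, or from a bodily injury that does not fit its explanation. Then, "if any of the above information leads staff to suspect abuse or neglect, steps are outlined for staff to obtain additional information". Staff also record what they learn and contact the study coordinator. The investigator reviews the information. If abuse is indicated, the coordinator reports it to protective services.

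**The concern.** A consent form's statement of when confidentiality will be broken is a promise about what happens to a disclosure. If the procedure behind it is wider, an adolescent or parent can disclose something without knowing that an outside report, or contact with the family, may follow. Such disclosures are foreseeable here. Most Aim 3 participants are minors, and the Measures section includes a family-functioning questionnaire answered by both parent and adolescent.

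The same two items head the training description, so staff and participants are given a shorter list than the procedure staff must carry out. The first item also rests on a statute cited by an abbreviation that the document never spells out or ties to the Dallas-Fort Worth sites or the University of Texas IRB.

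**Working it through.** No arithmetic applies. The check is to take each situation that the abuse procedure covers and see whether the consent description names it.

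| Situation | Named in consent as described | Named in training list | Opens internal inquiry (Abuse section) | Report to protective services (Abuse section) |
|---|---|---|---|---|
| Non-accidental bodily injury | Yes, item 1 | Yes | Yes | Yes, if abuse is indicated |
| Disclosed abuse with imminent physical danger | Yes, item 2 | Yes | Yes | Yes, if abuse is indicated |
| Disclosed past abuse, no injury and no imminent danger | No | No | Yes | Yes, if abuse is indicated |
| Disclosed current abuse that is not physical | No | No | Yes | Yes, if abuse is indicated |
| Suspected neglect | No | No | Yes | Not stated |

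Three steps follow from the table.

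1. **Disclosed abuse.** The verbal-disclosure source in the Abuse section has no condition on injury, imminence or type of abuse, and it expressly reaches back to past abuse. Rows three and four can therefore end in an outside report that neither consent item names. This is the firm part of the mismatch.
2. **Neglect.** The Abuse section tells staff what to do when they suspect neglect, but both of its listed sources concern abuse, and its protective-services sentence names abuse only. The introduction to Serious Adverse Events includes neglect; the earlier summary list under Description of Adverse and Serious Adverse Events has only abuse. The text thus supports inquiry and escalation on neglect but leaves open whether it is reported outside the study.
3. **Two channels under one label.** Mandatory Reporting Safeguards concerns reports to authorities. The later heading Mandatory Reporting, under Response procedures, introduces adverse and serious adverse events, which go to the investigator, the IRB and the NIH. No single list separates the two channels, so a reader cannot tell which triggers belong to which.

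**The case against.** The strongest reply is that the protocol bridges the gap itself. The Abuse section explains that abuse counts as serious because it is an imminent danger to the person, and imminent danger is the second consent item. Much disclosed abuse would then be covered. This stands in part. But the consent item is limited to physical harm, the bridging sentence is not in the wording described to subjects, and it does not fit abuse that is past or not physical.

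A reader might also infer several stronger things that the documents do not support:

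- **That training is limited to two items, so staff will miss cases.** The training list is introduced as non-exhaustive. The introduction to Serious Adverse Events describes wider training, and the Family crises item covers "extreme family disagreements, domestic violence, marital crisis, and mental illness". The most that can be said is that the list under the mandatory reporting guidelines does not name disclosed abuse or neglect.
- **That neglect is an outside-report trigger missing from the consent.** The documents do not say that neglect is reported outside the study.
- **That serious-event data will be incomplete.** Capture of serious events runs under the Response procedures, which name abuse and neglect, and does not depend on the consent list.
- **That the cited statute is the wrong one.** The documents show only that the abbreviation is undefined and not linked to the sites.

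**Conclusion.** The point holds as an inconsistency between the consent as described and the abuse procedure. Followed as written, the plan can send to protective services a verbal disclosure of abuse that fits neither reason subjects are said to be given. It can also open inquiry and escalation on suspected neglect without the consent description naming it. Participants may be incompletely informed. It would go too far to say they are misinformed: the consent form is not in the text reviewed, its wording may be fuller than the protocol's summary, and the content of the cited statute cannot be checked from the documents.

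In size, the gap is two situations absent from both the consent description and the training list: disclosed abuse without injury or imminent physical danger, and suspected neglect. Only the first is shown to lead to an outside report. The effect is on participant protection; no Aim 3 estimate is affected.

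**What to change.** Reconcile Mandatory Reporting Safeguards, Staff Training Safeguards, the introduction to Serious Adverse Events and the Abuse section into one list that:

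- separates what triggers internal inquiry and escalation from what triggers a report to authorities;
- says whether neglect is reported outside the study, and on what basis;
- says how past abuse, and abuse without injury, are handled.

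Use that list in the consent/assent form, the training material and the abuse procedure. Which triggers belong on it is for the sponsor and the IRB to settle. Spell out the ORS 419B citation and ask the IRB to confirm or correct it for the Dallas-Fort Worth sites.

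The cost is consent and training wording, in the English and Spanish versions that the protocol already promises, and one IRB amendment. No design, sample size or analysis change is needed.

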- **AIM 3. Pilot test of the MBS-supported intervention.** Based on work completed in study AIMS 1 and 2 we will conduct a 9-month pilot test of the MBS-supported intervention in AIM 3 among 20 adolescent patients meeting MBS/NIH qualifying criteria¹⁰ (class II obesity/120% of the 95th percentile and a co-morbidity, or class III obesity/140% of the 95th percentile according to CDC's age-and sex matched growth charts). Subjects will be enrolled up to 3 months (and not < 1 month) pre-MBS and for 6 months post-MBS. We will provide a water bottle at their first clinic visit. Upon completion of the surgery participants may receive a FitBit, a smart scale, workout bands, and weights to aid in their weight loss journey. *Recruitment.* Recruitment will take place in the outpatient suites of either the COACH or MBS Clinics which are located in the Children's Ambulatory Pavilion adjacent to the Children's Health (CH) System of TX main hospital. The COACH clinic currently has a waitlist of over 200 patients for obesity treatment programs and > 50% qualify for MBS. A total of 234 patients < 18 years old have been referred to MBS from 2016 to 2019.⁹²
- **Intervention Delivery.** After patient/parent consent is completed, participants will begin the pre-MBS intervention phase. A *minimum of 6 online sessions will occur pre-MBS, and 20 will occur post-MBS.* [name], MBS coordinator and a diabetes educator in Co-I [name]/[name]'s clinic will manage session delivery to adolescents/parents. All content will follow the DPP-adapted curriculum flow. After The RA will perform outreach, reminder calls, and follow-up for missed surveys or online content. Pre- and post-MBS intervention delivery (based on adapted curriculum/model) may consist of a combination of 1-on-1 and group sessions (in-person or virtually), and online support tools, dependent upon adolescent/parent qualitative feedback on delivery method preference.

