- **Statistical Power for AIM 3.** A single-factor, repeated measures design with a sample of 20 subjects, measured at baseline, 3-, and 6-months, achieves 80% power to detect a contrast using a multivariate T² test at a 0.01 significance level. We reduce the type I to a more conservative 1% to correct for multiplicity. The standard deviation across subjects at the same time point is assumed to be 1. The pattern of the covariance matrix is to have all correlations equal with a correlation of 0.25 between the first and second time point measurements.¹⁰⁰⁻¹⁰³ The value of the contrast applied to the hypothesized means is 1.⁹⁷ However, since we are anticipating an attrition rate of ~10%, we will recruit 22 adolescent MBS patients.

Data and Safety Monitoring

- *Data and Safety Monitoring:* All subjects will have an assigned unique study identification number used on all data forms and instruments. Data are computer-linked to the remainder of the dataset on

each individual, and linking information between personal identifiers and study numbers is kept in a locked file cabinet in the Principal Investigator's Office. Certain program staff (e.g., principal investigator, clinical team of [name], [name], and [name], study coordinator) will have access to confidential information needed to perform their respective duties, but the rest of the research staff are not privy to confidential information.

- *Potential Adverse Events.* None of the proposed procedures involve invasive methods of data collection. Most of the proposed methods are part of, or an extension of, the standard of care to assess pre-post MBS surgery mental and physical health and are minimal risk. These studies present minimal discomforts to the patient. Should any adverse events occur during this protocol, the medical facilities at University of Texas are prepared to care for the study participants. All participants will be debriefed regarding any serious health information that might be discerned in the protocol.
- *Description of Adverse and Serious Adverse Events:* Adverse events and serious adverse events identified for study participants that will be reported during protocol are: Adverse Events
 1. Family Crises
 2. Possible Violation of Confidentiality
 3. Extreme Distress due to Assessment Procedures
 4. Extreme Embarrassment or Distress in
Response to Disclosing Sensitive Personal Information

Serious Adverse Events

1. Suicidal Thoughts or Attempts
2. Abuse

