Participants' hospitalization (both for physical and psychiatric conditions) will be documented and reported (see reporting procedures for serious adverse events below).

5. Death

If a project staff member is advised of the death of a participant, the project staff member will document the death in the participant's study file and report the death to the PI.

Reporting procedures for adverse events

An Adverse Events and Serious Adverse Events form will be used to record any events.

The anticipated potential adversity inherent in assessment is limited to those situations described above and is addressed by the timely intervention of a licensed project facilitator skilled in risk assessment and mandatory reporting requirements.

The prevalence of adverse events described above will be reported both to our IRB and to NIH through annual progress reports. We will also report adverse events to others, as directed by our IRB or NIH Program Official.

Reporting Procedure for Serious Unanticipated Adverse Events

In the event of an unanticipated serious adverse event, the project PI will ensure that these events are reported to the NIH Program Official and the University of Texas IRB within 24 hours by phone, fax, and/or email and will submit a written report to the Program Official within two days. The project staff will utilize the following reporting procedures:

1. When the project staff and/or PI become aware of a serious adverse event, reporting requirements must be implemented in a timely manner.
2. PI completes a Serious Adverse Event Reporting Form and submit the form to the University of Texas IRB within two days. Serious adverse events include any hospitalizations or other life-threatening conditions (see serious adverse events above). All serious adverse events will be examined for the need for appropriate referral, an assessment of relatedness to the project, the need for any additional documentation and/or follow-up, and modification of the Informed Consent and notification of existing participants. All adverse events that are ongoing will be followed until they stabilize or resolve. [name] will resolve each adverse events or serious adverse event and will consult with the IRB, as necessary.
3. The PI will review the study protocol and determine what further action to take based on the best interests of the participants and of the research and submit to the IRB for approval.

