- Finally, a Data Safety Board will monitor all adverse events. Possible adverse events include those cases identified above as well as emotional distress associated with assessment or study participation. Adverse events will be reported to the chair of the committee as soon as possible and no later than 24 hours after they occur. Appropriate measures will be taken to ensure the participant's safety including referrals to primary care physician or supportive counseling provided by intervention staff. A summary of all adverse events will be sent to the chair of the Data Safety

Board every month. At least monthly, the Data Safety Board will review all adverse incidents via a face-to-face meeting. This committee will have the power to suspend recruitment to the study or discontinue the study entirely if they have concerns about the safety of the participants or the study itself.

Publication Plan

- Results from this study will be published in leading peer-reviewed journals. The PI anticipates a minimum of 6 final published manuscripts. These aggregate results will be available to research subjects and they will be made aware of their existence.

References

2. [name] SE, Xie L, Atem F, Mathew SM, [name] F, Schneider BE, Muñoz NC. Disparity Between United States Adolescent Class II and III Obesity Trends and Bariatric Surgery Utilization, 2015- 2018. *Ann Surg*. 2020 Sep 15. doi: 10.1097/SLA.0000000000004493. Epub ahead of print. PMID: 32941272.

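### The plan does not require non-serious physical injury or illness linked to the Aim 3 programme to be asked about or recorded

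*Combined protocol and SAP*

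**What the plan says.** The Adverse Events paragraph under Response procedures for adverse events sets the criterion: "Adverse events are those events that create distress for participants, such as (1) family crises; (2) possible violations of confidentiality". It goes on to distress from assessment and from disclosing sensitive information. The logging rule follows: "Adverse events that are not serious will be logged into the project's adverse events folder and noted in the participant's study file".

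The Description of Adverse and Serious Adverse Events, under Data and Safety Monitoring, introduces its list with "Adverse events and serious adverse events identified for study participants that will be reported during protocol are". It then names four non-serious kinds and five serious kinds.

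Reporting procedures for adverse events states the expected harm: "The anticipated potential adversity inherent in assessment is limited to those situations described above". The Data Safety Board paragraph, just before the Publication Plan, says: "Possible adverse events include those cases identified above as well as emotional distress associated with assessment or study participation".

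On exposure, the Aim 3 text under Study Measures says: "Upon completion of the surgery participants may receive a FitBit, a smart scale, workout bands, and weights to aid in their weight loss journey". Intervention Delivery sets a "minimum of 6 online sessions will occur pre-MBS, and 20 will occur post-MBS".

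**The concern.** The adverse event text is written mainly around the risks of being assessed: distress, embarrassment, disclosure and loss of confidentiality. Aim 3 also delivers a lifestyle programme to adolescents before and after surgery, and may put exercise equipment in their homes. A strain or a fall while using a supplied weight is a foreseeable kind of non-serious harm. Staff who follow the definition and the list would find no category for it and no instruction to ask about it.

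What is at stake is how the safety record can be read. This is the first test of an adapted programme. If the final report shows no physical adverse events, a reader could not tell whether none happened or whether nobody asked. Minor events that are not asked about at the time are hard to recover later.

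**Working it through.** No arithmetic lies behind this point beyond a count, and the plan gives no figure to reproduce. The check sets the safety passages beside the exposure passages.

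1. **Definition** (Response procedures, Adverse Events). The criterion is distress. The examples are offered as illustrations, so the list there is not strictly closed, but an injury that upsets nobody does not meet the criterion.
2. **Reportable list** (Description of Adverse and Serious Adverse Events). The four non-serious entries are family crisis, possible confidentiality breach, extreme distress from assessment, and extreme embarrassment or distress from disclosure. Physical entries: 0 of 4. The introductory wording reads as a complete list.
3. **Expected harm** (Reporting procedures). It is tied to assessment and limited to the situations already described. The annual reports to the IRB and NIH cover the adverse events so described.
4. **Data Safety Board paragraph.** It refers back to the same cases and adds emotional distress from assessment or participation. It names no physical event.
5. **Mandatory reporting** (Staff Training Safeguards). Physical injury appears only as "physical injury to any study subject caused by other than accidental circumstances", which leaves out an accident during exercise.
6. **Other data sources.** The problem form under Procedures to safeguard against adverse events covers what staff notice while collecting data. The record extraction under Study Procedures takes BMI, comorbidity and social-determinant data. The Process Measures cover acceptability, feasibility and sustainability. None of these asks about injury or illness.
7. **Exposure** (Study Design, Incentives, Study Measures). Bands and weights may be supplied after surgery. The planned sessions number at least 6 + 20 = 26 per participant.
8. **Serious route.** A physical event clearly enters the plan only if it is serious. Even here the text disagrees with itself. The list under Data and Safety Monitoring describes hospitalization as psychiatric or drug related. The Hospitalization item under Response procedures covers both physical and psychiatric admissions, and the reporting procedure for serious unanticipated events refers to any hospitalization.

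Items 1 to 6 contain no requirement to ask about or record a non-serious physical event, item 7 shows that the programme can give rise to one, and item 8 shows that the serious route does not fill the gap.

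**The case against.** The strongest reply is that the plan is more open than the list suggests. The definition offers examples only, and an injury that distresses a teenager fits it. The same section opens with a duty to report potentially harmful events. The adverse event form is for any events, and the Oversight paragraph says its review is not confined to the events it names. The medical facilities are said to be ready to care for participants should adverse events occur, which suggests that medical events were in mind. The text also reaches beyond assessment in places: the Board paragraph mentions distress from participation, and the family crisis item mentions a crisis arising from the curriculum tools. All of this stands. It shows that an injury could be logged. It does not show that anyone must ask, or that the event would be counted consistently from one participant to the next.

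Three stronger readings are tempting, and the documents do not support them.

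- A reader might infer that such events would never be recorded. The open wording just described rules that out; the accurate statement is that recording is not required.
- A reader might infer that the Data Safety Board can act only on events that fit the definition. The plan lets the Board suspend recruitment or stop the study on any concern about participant safety or the study itself.
- A reader might infer that the feasibility and acceptability conclusions would rest on a false safety record. Process Measures defines feasibility by recruitment, retention and adherence, and acceptability by how appropriate, interesting and easy to use the content is. Neither uses adverse event counts.

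It is also fair to say that the exposure is partly conditional. Equipment is something participants may receive, and session content is not set out. That the sessions include activity and diet advice is inferred from the description of a lifestyle curriculum adapted from the DPP. The attached grant application, which might say more, is not among the documents reviewed.

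**Conclusion.** The point holds as a gap in systematic capture. The definition turns on distress, none of the four listed non-serious kinds is physical, and no passage tells staff to ask about non-serious physical harm. A report of no such events would therefore be uninformative.

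The count of 0 in 4 needs no assumption. The relevance of the gap rests on the bands and weights actually being supplied, or on the sessions containing activity or diet content. The documents give no injury rate for this population, so the number of events at risk of being missed cannot be stated.

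The weight is moderate. Aim 3 is a proof-of-concept study in about 20 participants, with no safety endpoint or safety hypothesis, and the gap changes no estimate, test or stated outcome. It is a recommended improvement to participant safety and to the reading of the results, not a fault on which the study's validity depends.

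**What to change.** - In the Description of Adverse and Serious Adverse Events, the Adverse Events paragraph under Response procedures, and the Data Safety Board paragraph, add one non-serious category: physical injury or illness that occurs during a session, supplied-equipment use or programme activity, or that the participant or parent attributes to a session, supplied equipment or programme content.
- Ask about it with one standard question in the short surveys already embedded in the sessions and in the 3- and 6-month surveys. If every session carries one survey, that is at least 26 + 2 = 28 occasions per participant.
- Log the answers and tabulate them with relatedness to the programme, using the same kind of assessment the plan already makes for serious events.
- Reconcile the passages on hospitalization, so that staff have one statement of which admissions are reportable. Which scope applies is for the investigator and the IRB.

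The cost is some protocol wording and one added question in existing surveys. The drawback is more events to log, many of them part of surgical recovery and not due to the programme. Aim 3 describes one group, so the relatedness judgement will separate the two only imperfectly. Clinical handling of any event stays with the investigator.
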